This study in no way alters the patient's clinical management or care pathway. During colonoscopy in the presence of polyp(s) <20 mm, an observation sequence and image acquisition are performed in NBI, which does not significantly alter the duration of the endoscopic examination. The NBI is integrated into the high-definition endoscope (Olympus, Fujifilm) and the transition from white light to NBI is instantaneous.

Type I Hyperplasique

Type II Adénome

Figure 1: NICE (Narrow band imaging International Colorectal Endoscopic) **classification.** Diagnostic criteria in favor of a typical hyperplastic polyp (type I) are: a) absence of dark appearance of the polyp in relation to the adjacent mucosa, b) absence of brownish vessels, c) absence of oval structures within the polyp.

Conversely, the presence of one or more of the above-mentioned criteria is indicative of a conventional adenomatous polyp (type II).

Figure 2: WASP (Workgroup Serrated PolypS and Polyposis) **classification**. Diagnostic criteria in favor of an adenomatous scalloped polyp are: a) the existence of a cloudy appearance of the polyp, b) an irregular shape, c) the presence of black spots within the colonic glands.

CONECCT	IH Hyperplasique	IS Lésion festonnée sessile	IIA Adénome simple	IIC Adénome à risque ou cancer superficiel	III Adénocarcinome profond
Macro	Souvent petits <10 mm Surélevé Ila	Paris IIa ou IIb Limites imprécises en nuage ou en plateau	Paris Ip, Is Ou Ila Rarement déprimé	Souvent IIc Ou IIa + IIc Ou LST Non granulaire Ou macronodule (> 1cm) sur LST Granulaire	Souvent III Ou IIc avec composant nodulaire dans la dépression Saignements spontanés
Couleur (NBI ou équivalent)	Claire ou équivalente au background	Variable Mucus jaune (rouge en NBI)	Foncée par rapport au background	Foncée souvent	Hétérogène, foncées ou très claires par zones
Vaisseaux (NBI ou équivalent)	Absence de vaisseaux ou vaisseaux fins ne suivant pas les cryptes	Absents parfois Spots noirs au fond des cryptes rondes	Réguliers Suivant les cryptes allongées	Irréguliers mais persistants Pas de zone avasculaire	Irréguliers Gros vaisseaux interrompus Ou absents (zones avasculaires)
Cryptes (chromo virtuelle ou réelle)	Rondes Blanches	Cryptes rondes points noirs (NBI)	Allongées Ou Branchées Cérébriformes régulières	Irrégulières mais conservées Pas de zone amorphe	Absentes Détruites Ou irrégulières dans une zone délimitée (démarcation nette)

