2.2 Objectives and secondary endpoints

2.2.1 Secondary objectives

 Measurement of diagnostic performance indices (specificities, PPV, NPV) using NBI and white light alone for characterization of polyps CONECCT IH and IS versus CONECCT IIA

Within scalloped polyps (according to pathological analysis results), diagnostic capabilities (sensitivities, specificities, PPV, NPV) of NBI and white light alone to characterize CONECCT IS polyps.

- Comparison of the diagnostic performance of NBI and white light alone for the characterization of polyps CONECCT IH and IS versus CONECCT IIA
- Diagnostic performance by degree of certainty in NBI.
- Evaluation of the role of endoscopist seniority in polyp characterization in NBI.
- Assessment of the role of polyp size in polyp characterization.

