5.2 Statistics

Responsible for statistical analysis: [name] [name]

5.2.1 Description of planned statistical methods, including schedule of planned interim analyses and statistical justification of number of inclusions

Analysis of primary endpoint:

Sensitivity of the NBI technique to pathological findings for the characterization of colonic polyps (conventional adenomatous [CONECCT IIA] versus scalloped [CONECCT IS]) at colonoscopy will be calculated with its 95% confidence interval.

Secondary endpoints :

- The diagnostic performance (specificity, positive predictive value, negative predictive value, RV+, RV-, diagnostic accuracy (corresponding to the rate of correct responses)) of NBI for the characterization of colonic polyps (conventional adenomatous [CONECCT IIA] versus scalloped [CONECCT IS]) compared with standard histology will be estimated with their 95% confidence interval.

- The sensitivity and specificity of white light compared with standard histology results will be estimated with a 95% confidence interval and compared with those obtained by NBI using a McNemar test.

- If numbers permit, sensitivity analyses will be carried out:

- The sensitivity of NBI for the characterization of CONECCT IH and IS polyps versus CONECCT IIA will be estimated according to the certainty of the polyp characterization in NBI: strong or weak. These 2 sensitivities will be compared using a Chi2 test.

- The same analysis will be carried out on the seniority of the endoscopist: junior or senior.

- The same analysis will be performed according to polyp size: 1-5mm vs. 6-9mm vs. 10-20mm or 1-5mm vs. 6-20mm depending on numbers.

Number of subjects required :

Over 48 months, we plan to include 690 patients at Nantes University Hospital and the CHD de Vendée, with the aim of characterizing at least 690 polyps measuring less than 20 mm. About 50% of these will be CONECCT IIA polyps, 40% CONECCT IH and 10% CONECCT

IS. In addition, a majority of these polyps will be <5 mm in size (\approx 60%), \approx 30% between 6-9 mm and \approx 10% >10mm.

Assuming that 5% cannot be analyzed, and that the sensitivity of the NBI is 90%, we can estimate our sensitivity with a confidence interval of \pm 3%.

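### The comparisons by certainty, endoscopist seniority and polyp size test sensitivity alone, so they cannot separate better discrimination from a readier scalloped call, and they cannot see a difference in specificity.

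*Combined protocol and SAP*

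**What the plan says.** Three of the secondary objectives in section 2.2.1 concern factors that may affect NBI reading: "Diagnostic performance by degree of certainty in NBI", "Evaluation of the role of endoscopist seniority in polyp characterization in NBI" and "Assessment of the role of polyp size in polyp characterization". The first speaks of diagnostic performance; the other two speak of a role in characterization.

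Section 5.2.1 answers all three with one measure, on condition that numbers permit. For certainty: "The sensitivity of NBI for the characterization of CONECCT IH and IS polyps versus CONECCT IIA will be estimated according to the certainty", strong or weak, followed by "These 2 sensitivities will be compared using a Chi2 test". For the other two factors: "The same analysis will be carried out on the seniority of the endoscopist: junior or senior" and "The same analysis will be performed according to polyp size". Section 5.2.2 sets significance at p < 0.05.

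Specificity, predictive values, likelihood ratios and accuracy are planned in section 5.2.1 for NBI overall, and nowhere by these three factors. For white light versus NBI, the same section compares both sensitivity and specificity.

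**The concern.** Sensitivity uses only the polyps that histology calls scalloped. It rises when a reader discriminates better, and also when a reader simply says scalloped more often. In the second case specificity falls, and an analysis confined to sensitivity does not show the fall.

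Two errors follow. A group with a more liberal threshold can show significantly higher sensitivity although its discrimination is the same. And two groups with equal sensitivity but different specificity will look alike. In both cases the result does not answer an objective framed as diagnostic performance, or as the role of a factor in telling scalloped from conventional adenomatous polyps.

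**Working it through.** **Inputs from section 5.2.1.** 690 polyps; 5% not analyzable; 50% IIA, 40% IH, 10% IS; expected NBI sensitivity 90%. Significance at 0.05 (section 5.2.2), taken as two-sided.

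**Group sizes and the plan's own figure.** Scalloped polyps (IH plus IS): 690 × 0.95 × 0.50 ≈ 328. IIA polyps: also about 328. The half-width of the 95% interval on 328 is 1.96 × √(0.90 × 0.10 / 328) = 3.25%, which agrees with the stated ±3% to a whole percent. That figure does not bear on this point; it confirms the denominators. An even split gives 164 scalloped and 164 IIA polyps per group.

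**Assumptions not in the documents.** Equal-variance binormal model; specificity 90% at the neutral threshold; even split; independent polyps; the two groups' thresholds displaced by c SD in opposite directions from neutral.

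**Case 1: equal discrimination, different thresholds.** With z(0.90) = 1.2816, sensitivity is Φ(1.2816 ± c) in the two groups, and specificity takes the same two values in reverse order. Accuracy at the planned 50/50 mix is therefore the same in both groups. Power of the two-proportion test is Φ[(|Δ| − 1.96 s₀)/s₁], where s₀ is the pooled and s₁ the unpooled standard error.

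| c | Sensitivity, group 1 vs 2 | Accuracy in both | Chi2 significant |
|---|---|---|---|
| 0.10 | 91.6% vs 88.1% | 89.9% | 18% |
| 0.15 | 92.4% vs 87.1% | 89.7% | 35% |
| 0.20 | 93.1% vs 86.0% | 89.6% | 55% |
| 0.25 | 93.7% vs 84.9% | 89.3% | 74% |

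For c = 0.25: Δ = 0.0883, s₀ = √(2 × 0.893 × 0.107 / 164) = 0.0341, s₁ = √[(0.937 × 0.063 + 0.849 × 0.151)/164] = 0.0338, and Φ[(0.0883 − 0.0669)/0.0338] = Φ(0.63) ≈ 0.74.

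A simulation of 20,000 trials tells the same story. With sensitivity 95% vs 85%, specificity 82.1% vs 93.7% and equal discrimination (AUC 0.965 in both), the planned test was significant in 88% of trials at a 50:50 split and 78% at 30:70. With 93% vs 87% the figures were 45% and 34%. A test on sensitivity and specificity together was significant in about 4% to 5% throughout.

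**Case 2: equal sensitivity, different specificity.** Sensitivity 90% in both groups; specificity 90% vs 75%. The planned test rejects about 5% of the time, which is chance. For specificity on 164 IIA polyps per group: s₀ = √(2 × 0.825 × 0.175 / 164) = 0.0420, s₁ = √[(0.90 × 0.10 + 0.75 × 0.25)/164] = 0.0411, and Φ[(0.15 − 0.0822)/0.0411] = Φ(1.65) ≈ 0.95.

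**The case against.** Sensitivity is the primary endpoint, so breaking it down by factor is a recognizable choice. The analyses are secondary and conditional on numbers, no decision rule depends on them, and overall specificity is planned. A significant result would be a correctly labelled difference in sensitivity. All of this stands and limits the weight of the point, but it does not supply the missing half of what section 2.2.1 asks for.

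The illustration has limits too. Strong and weak are labels that one endoscopist puts on individual calls, so a threshold shift between reader groups is a poor model for certainty; it fits seniority better. The figures also depend on the split. If the size contrast fell at 10 mm and the histology mix were the same in each band, the 90/10 expectation in section 5.2.1 would give about 295 vs 33 scalloped polyps, and even c = 0.25 would give at most about 47%. Up to 4 polyps per patient (section 3.1) would change the figures further.

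A reader might infer that bias is built into the size comparison, because the CONECCT table in section 1.1 lists "Souvent petits <10 mm" as a feature of IH. The documents do not support that:

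- The cue belongs to IH only, while the analysis pools IH with IS. A larger polyp not called IH can be called IS and still count as scalloped.
- The IIA column gives no size.
- About 90% of the expected polyps fall under 10 mm, so the cue cannot separate 1-5 mm from 6-9 mm.

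Nor do the documents say that a sensitivity difference will be reported as a difference in performance; the plan leaves that reading open.

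**Conclusion.** The point holds as a gap between objectives and analysis. For certainty the mismatch is explicit: performance is asked for and sensitivity is planned. For seniority and size the objective is worded more loosely, but the limitation is the same. By the plan's own standard for white light versus NBI, specificity belongs in the comparison.

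The size is illustrative. With equal discrimination, the planned test would be significant about 18% to 74% of the time for shifts of ±0.10 to ±0.25 SD at 164 scalloped polyps per group, and a specificity of 90% versus 75% would go unseen. These figures rest on the binormal model, the assumed 90% specificity, an even split and independent polyps. They show what can happen, not what will. The primary endpoint is not affected. The change is worth making because it is nearly free.

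**What to change.** In section 5.2.1, for certainty, seniority and size:

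1. Estimate specificity among histological IIA polyps with its 95% confidence interval, and compare it between groups alongside sensitivity.
2. State in advance how the pair will be read. Differences in opposite directions indicate a difference in calling threshold. A group is described as performing better only if one measure is better and the other is not worse, judged from the confidence interval of the difference rather than from a non-significant p-value, or if a joint measure differs.
3. If a joint measure is used, name it: for example, the histology-by-factor interaction in a model of the NBI call, allowing for clustering by patient and, for seniority, by endoscopist. This is not interchangeable with two separate comparisons: under a pure threshold shift both measures differ while the interaction is close to nil.

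The cost is a few lines of analysis text and some table rows, on data already collected. About 328 IIA polyps are expected, as many as scalloped, so numbers that permit the sensitivity comparison should broadly permit this one. The downside is a few more exploratory comparisons, which should be labelled as such.

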2.2.2 Secondary endpoints

1-2 Polyp characterization using white light according to CONECCT classification Polyp characterization using NBI according to CONECCT classification Polyp characterization using standard histology according to CONECCT classification

3- Evaluation of the degree of certainty of characterization after examination by: strong or weak

4- Endoscopist seniority: junior or senior: <2000 vs \ge 2000 colonoscopies performed.

5- Polyp size defined on NBI examination: 1-5mm vs 6-9mm vs 10-20mm

3. Study population

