4.2.2 Description of techniques and analyses

Study diagram :

- All endoscopists participating in the study will receive an initial one-hour training course in NBI polyp characterization, delivered by an expert endoscopist in image analysis ([name] [name], graduate of the DIU 'Endoscopie Diagnostique Avancée').
- A verification test (rate of correct answers >95%) will be carried out before each operator is authorized to take part in the study, based on an independent set of images of 30 colonic polyps.
- Each patient corresponding to the pre-inclusion criteria and agreeing to take part in the study is "pre-included". During colonoscopy, the presence of any polyp(s) smaller than 20mm is determined. The right colon, which is the preferred site for adenomatous scalloped polyps, will be examined with particular attention by a second pass under white light. This 2^{ème} pass is routinely performed in standard practice, for example to check fast-moving areas during colonoscopy, and will only increase examination time by around 2-3 minutes. Patients without a polyp smaller than 20 mm are not included in the study.

- Each polyp measuring less than 20mm will be analyzed in white light and NBI, as follows:
- 1) White-light image analysis

2) Switch to NBI mode by simply pressing the 'NBI' button on the endoscope handle (immediate acquisition of the NBI image with photographic recording in LB and NBI). A prediction of the histological type of polyp according to the CONECCT classification is made by the endoscopist and noted in the CRF, together with the degree of certainty (strong or weak).

The study is limited to 4 polyps per patient. Only data from the first 4 polyps removed will therefore be collected.

- All polyps detected and analyzed by NBI are then removed by excision (forceps excision, mucosectomy) according to the usual procedure and analyzed by conventional histology (gold standard).
- If it is impossible to characterize a polyp by NBI (image of poor quality or diagnosis impossible), the examination will be considered a technical failure of NBI, but the polyp will be removed for histological analysis in accordance with current recommendations.
- If the polyp is not recovered for histological analysis, or if interpretation is impossible (coagulation artifacts after standard resection, for example), the examination will be considered a technical failure of standard histology.

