5.2.2 Expected statistical significance

A p-value < 0.05 is considered statistically significant.

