5.2.5 Choosing the people to include in analyses

All polyps < 20mm characterized by NBI and standard histology of included patients will be analyzed.

6. Vigilance and management of undesirable events

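### The junior versus senior comparison uses a polyp-level Chi2: if endoscopists within a seniority group differ in accuracy, the uncorrected test has a false-positive rate above 5%

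*Combined protocol and SAP*

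**What the plan says.** The role of seniority is a secondary objective (section 2.2.1): "Evaluation of the role of endoscopist seniority in polyp characterization in NBI". Section 2.2.2 defines the factor as "Endoscopist seniority: junior or senior", with the cut at 2000 colonoscopies performed. It is therefore an attribute of the person.

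Section 5.2.1 sets out the analysis in three steps, under a heading that makes it conditional on sufficient numbers:

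- For degree of certainty: "The sensitivity of NBI for the characterization of CONECCT IH and IS polyps versus CONECCT IIA will be estimated" in each certainty group.
- Then: "These 2 sensitivities will be compared using a Chi2 test".
- For seniority: "The same analysis will be carried out on the seniority of the endoscopist: junior or senior".

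Section 5.2.5 makes the polyp the unit: "All polyps < 20mm characterized by NBI and standard histology of included patients will be analyzed". Section 4.2.2 makes the endoscopist the reader: "A prediction of the histological type of polyp according to the CONECCT classification is made by the endoscopist". Section 5.2.2 sets the threshold: "A p-value < 0.05 is considered statistically significant".

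No section provides a random effect, GEE, robust variance or other allowance for polyps read by the same endoscopist. Section 5.2.1 does not say whether the Chi2 carries a continuity correction.

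**The concern.** All polyps read by one endoscopist carry the same seniority label and depend on the same person's skill. If skill varies between endoscopists of equal seniority, twenty polyps from one reader are not twenty independent pieces of evidence about seniority. Much of the information then lies in the number of endoscopists, while the Chi2 takes its variance from the number of polyps.

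A few unusually good or poor readers in one group could thus produce a p-value below 0.05 with no seniority effect at all. That matters because the study's declared interest is performance by non-expert endoscopists, and a seniority effect would be read as information on who can use the technique in community practice.

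**Working it through.** **Inputs from section 5.2.1.** 690 polyps; 5% not analysable; 50% IIA, 40% IH, 10% IS; sensitivity 90%. The seniority analysis takes IH and IS together as positives: 690 × 0.95 × 0.50 = 327.75, about 328.

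**The plan's own figure.** The half-width 1.96 × √(0.90 × 0.10 / 328) is 3.25%, which rounds to the stated ±3%. So 328 fits the plan's arithmetic, and that arithmetic treats polyps as independent.

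**Assumptions, because the documents are silent.** K endoscopists (12, 30 or 50), half of them junior, with equal workloads. ICC of 0.02, 0.05 or 0.10 within seniority group. At 90% sensitivity the between-reader SD is √(ICC × 0.09), that is 4.2, 6.7 or 9.5 percentage points.

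**Formula.** Design effect DE = 1 + (328/K − 1) × ICC. False-positive rate = 2 × [1 − Φ(1.96/√DE)]. Example, K = 12 and ICC 0.05: DE = 1 + 26.33 × 0.05 = 2.32; 1.96/√2.32 = 1.29; rate 19.8%.

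| K | DE at ICC 0.02 / 0.05 / 0.10 | Uncorrected Chi2, formula | Continuity-corrected Chi2, simulated |
|---|---|---|---|
| 12 | 1.53 / 2.32 / 3.63 | 11.3 / 19.8 / 30.4% | 8.5 / 15.6 / 25.8% |
| 30 | 1.20 / 1.50 / 1.99 | 7.3 / 10.9 / 16.5% | 4.9 / 7.7 / 12.7% |
| 50 | 1.11 / 1.28 / 1.56 | 6.3 / 8.3 / 11.6% | 4.0 / 5.8 / 8.5% |

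Beta-binomial simulations of the uncorrected Chi2 agree with the formula to within about 1.5 points; the highest value for 30 endoscopists at ICC 0.10 was 18%. At ICC 0 the uncorrected test holds its level (4.9% to 5.2%) and the corrected one is conservative (about 3%). Workloads that vary independently of seniority raise the uncorrected rates to 13/24/35%, 8.5/14/21% and 7/10/15% for 12, 30 and 50 endoscopists.

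**Checking remedies.** An unweighted t-test on endoscopist-specific sensitivities holds 4.1% to 5.1% when workload is unrelated to seniority. It fails when juniors read fewer polyps. With one third junior and each senior reading three times as many polyps (an assumption), at ICC 0.02 to 0.10:

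- 30 endoscopists: t-test about 8% to 11%, uncorrected Chi2 6.0% to 11.0%.
- 50 endoscopists: t-test about 9% to 11.5%, Chi2 5.5% to 8.6%.
- 12 endoscopists: t-test 8.7% falling to 5.3%, Chi2 8.3% rising to 20.0%.

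Juniors then have few positives each, and their unweighted proportions near 90% are skewed and unequally variable. A two-proportion test that keeps polyp weighting, scales the variance by an overdispersion factor not below 1, and refers to t on K − 2 degrees of freedom stayed at about 2% to 6% in all settings tried.

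**The case against.** Five points can be made for the plan.

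- **The size rests on two unknowns.** This stands. The protocol speaks of a large population of endoscopists, which favours the lower rows of the table. With 30 to 50 endoscopists, ICC 0.02 and equal workloads, the excess is only 1 to 2 points.
- **The entry test makes readers alike.** Section 4.2.2 requires more than 95% correct on 30 images, so at least 29. This may lower the ICC but does not show it to be zero: 29/30 has an exact 95% interval of about 83% to 99.9%, and the test uses an image set rather than live colonoscopy.
- **A continuity correction may be intended.** It would keep the rate at or below 5% in mild settings (30 or 50 endoscopists, ICC 0.02, equal workloads), but not at ICC 0.05 or more in the table above.
- **The analysis is minor.** This stands. It serves one secondary objective and is run only where numbers allow.
- **The obvious repair can be worse.** This also stands: the unweighted t-test is not a safe default, and it replaces a polyp-level quantity with an average over endoscopists.

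A reader might also infer that any difference between readers breaks the test. The relevant variation is within seniority groups; a pure junior-senior difference causes no inflation. Nor can it be inferred that endoscopist identity is not recorded. Section 4.4 lists only source data outside the medical record, and section 5.1.1 has the endoscopist complete a form for each polyp. Confirmation is all that can be asked.

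**Conclusion.** The point holds conditionally. The planned test ignores clustering by endoscopist for a factor fixed at endoscopist level. If readers within a seniority group differ in accuracy, the uncorrected Chi2 exceeds the 5% threshold of section 5.2.2. Under the assumptions stated (328 positives, 90% sensitivity, half junior, equal workloads, ICC 0.02 to 0.10), the rate is about 6% to 18% with 30 to 50 endoscopists and 11% to 30% with 12.

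The direction is firm for the uncorrected test; the amount is illustrative. The documents do not support a claim that this trial's error rate will be 20% or 30%, because those values need few readers, a high ICC or very uneven workloads. Nor does the point alter the primary sensitivity estimate. It is a low-priority correction, worth making because it is cheap.

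**What to change.** In section 5.2.1:

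1. Replace the seniority Chi2 with a comparison that treats the endoscopist as a cluster and keeps polyp weighting. One option is a logistic model with an overdispersion scale not below 1 and a t reference on (endoscopists minus 2) degrees of freedom; it was checked here in the form of the scaled two-proportion test. A mixed logistic model is an alternative whose error rate was not simulated.
2. Do not make an unweighted t-test on endoscopist-specific sensitivities the default.
3. State that, if either group has too few endoscopists, their individual sensitivities will be reported descriptively without a p-value.
4. Confirm that a coded endoscopist identifier is available in the analysis data.

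The cost is a few sentences and at most one coded field, with no change to patients, procedures or recruitment. The real downside is lower apparent power. As a rough guide only, simulated with the endoscopist-level t-test for a true 85% versus 95% at ICC 0.02/0.05/0.10, power was 62/47/32% with 12 endoscopists, 79/69/58% with 30 and 82/77/69% with 50. The power of the scaled test was not computed.
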